## LIST OF ABBREVIATIONS AND ACRONYMS

AE	Adverse event
BILAG	British Isles Lupus Assessment Group
COVID-19	Coronavirus disease 2019
CRA	Clinical research associate
DDI	Drug-drug interaction
eCRF	Electronic case report form
FDA	(US) Food and Drug Administration
GCP	Good Clinical Practice
HMA	(EU) Heads of Medicines Agencies
IB	Investigator's Brochure
ICH	International Council for Harmonisation
IEC	Independent Ethics Committee
IRB	Institutional Review Board
PD	Protocol deviation
PGA	Physician's Global Assessment
PRO	Patient Reported Outcome
QoL	Quality of Life
SARS-CoV-2	Severe acute respiratory syndrome coronavirus 2
SLE	Systemic lupus erythematosus
SLEDAI-2K	Systemic Lupus Erythematosus Disease Activity Index-2000
SRI	Systemic Lupus Erythematosus Responder Index
WBC	White blood cell
WHO	World Health Organization

## UPDATE TO THE ADDENDUM

This amendment applies to the addendum, dated 8 April 2020, to the protocol ID-064A202, issued to implement “Exceptional measures to ensure subject safety and counteract potential trial conduct disruption due to the COVID-19 pandemic”.

The resulting document is: Addendum 2 to protocol ID-064A202, dated 27 May 2020.

### **Rationale**

The main reason for the changes to the addendum is to implement the IDMC recommendations sent to Idorsia on 18 May 2020, consisting of screening all new patients for SARS-CoV-2 prior to entry in study ID-064A202. Hence, subjects who test positive for SARS-CoV-2 should be considered as screen failures and discontinued from the study.

### **Changes to the Addendum**

The section “Subjects infected with SARS-CoV-2” of the addendum is updated to include the following new instructions:

#### **2.3 Subjects infected with SARS-CoV-2**

- During screening, subjects must be tested for SARS-CoV-2 unless the subject has tested negative within a week prior to screening. Subjects will be screen failed and discontinued from screening if she/he tests positive for SARS-CoV-2.
- It is the responsibility of the investigator/delegate to obtain the subject’s consent using a specific ICF if the testing for SARS-CoV-2 is performed as part of the trial-mandated procedures during screening. The SARS-CoV-2 test can be performed at the site or in a local laboratory using a prescription provided by the investigator.
- After subject randomization, testing for SARS-CoV-2 should follow local guidance.

### **Two versions of the updated addendum will be provided:**

1) a clean version and 2) a comparison document showing deletions and insertions in comparison to the previous addendum version.

## 1 INTRODUCTION

As a consequence of the pandemic of respiratory infectious disease (COVID-19; declared a pandemic by the WHO on 11 March 2020) caused by a novel coronavirus (SARS-CoV-2), Idorsia provided instructions and guidance in communication letters sent to ID-064A202 (CARE) study investigators on 19 March 2020 and 31 March 2020. These measures and instructions are in line with health authority guidelines (FDA, HMA and individual national health authorities) released in March 2020 on how to address the challenges caused by the pandemic itself.

These measures, which also constitute PDs, are introduced to preserve subject safety, trial integrity and interpretability, as well as compliance with regulatory requirements.

Idorsia tracks these deviations from the protocol as “PDs related to COVID-19”. This will allow, at the end of the trial, a reconstruction of the impact that such deviations had on the trial integrity and interpretability. This requires that the instructions and measures included in this addendum continue to be collected as PDs as per original protocol definition, and will be identified as due to COVID-19 even after the implementation of this addendum.

The objective of this addendum is to document those measures and instructions in the protocol. The addendum applies **to those sites affected by the COVID-19 outbreak and is limited to the time during which such sites are affected.**

This addendum is therefore limited in scope and in duration.

The recommendations and instructions that have been provided to the investigators are described below with reference to the protocol sections affected:

## 2 RECOMMENDATIONS AND INSTRUCTIONS

### 2.1 Conduct of on-site visits

For subjects who are continuing to participate in the ID-064A202 (CARE) study, it is important that the protocol visit schedule is adhered to in order to ensure subject safety and trial integrity during the COVID-19 pandemic outbreak.

The preferred option is to maintain on-site visits, provided that the subject is allowed and can travel to the site [see protocol section 7.1]. To ensure safety of the subject on his/her way to the site, the site staff will remind the subject to adhere to local laws and recommendations (e.g., not using public transportation). Alternatively, subjects can use taxis or private cars, the cost of which will be reimbursed by Idorsia.

On-site visits should be performed according to the protocol [see protocol section 7.2, table 4]. To facilitate on-site visits, scheduled visits might be brought forward or visit windows extended (e.g.,  $\pm 7$  days from scheduled visit, or even longer if the subject has enough study treatment). The reason for this delayed scheduled visit must be documented in the subject’s medical chart.

If the subject can travel to the investigational site for his/her study site visit, the investigator should:

- Ensure the subject's safety on his/her way to the site in compliance with local/country instructions (e.g., not using public transportation).
- Perform the on-site visit assessments according to the protocol [protocol section 7.1 and 7.2].
- If blood and urine samples cannot be collected by the courier for shipment to the central laboratory, the analysis can be performed by the site's local laboratory\*.

\*If done by site local laboratory, the investigator should make sure that the site personnel has an "unblinded" staff member who is not involved in the conduct of ID-064A202 (CARE) study and who can check for any WBC (including differentials) and lymphocyte counts and redact these parameters from the laboratory report. If this option is not available, the site local laboratory analysis should still be performed.

**Note that new subjects may be considered for screening only after thorough evaluation of the benefit-risk for the subject participation in the context of the COVID-19 pandemic. Screening visit should only take place if a complete on-site visit can be organized. If this is not possible, the preferred option is to reschedule the screening visit to a time when all components of the site visit can be performed in full compliance with the protocol.**

## 2.2 Conduct of home visits or remote visits

If the subject cannot, is not allowed, or is not willing to travel to the investigational site due to the COVID-19 pandemic, **remote visits (telephone call or video call)** may be conducted as described below.

- If possible, it is preferable to have the remote visit performed as a **video call** instead of a telephone call.
- The IEC or IRB must be notified in advance of remote visits if this is a local requirement.
- **During the remote visit**, the investigator will interview the subject to:
  - Check for the occurrence of any new AE or worsening of existing ones. When asking for AEs, the same process as that used for site visits is to be followed [see protocol section 9.3], i.e., use open-ended questions such as "Have you had any new symptoms or experienced any worsening of your disease since the last study visit?".
    - If the subject spontaneously reports symptoms of worsening of disease activity or symptoms that could be related to the safety areas of special interest [refer to protocol appendix 5] follow the instructions below, as relevant:

- Symptoms potentially related to SLE flare: a visit by site staff / or home nurse to the subject's home should take place if allowed or the subject should be asked to come to the site if this is allowed in emergency cases.
  - Bradycardia (e.g., dizziness, vertigo, syncope): treatment medication interruption and restart should be verified, and the subject should be asked to check their pulse. If severe bradycardia is suspected, a visit by site staff / home nurse to the subject's home should take place if allowed.
  - Hypertension/hypotension (e.g., severe headache, fatigue, confusion, vision problems, chest pain, difficulty breathing, irregular heartbeat, dizziness or lightheadedness, fainting): the subject should be asked about availability of a home-based automated blood pressure instrument for self-assessment or such a device should be delivered to the subject's home.
  - Dyspnea: if severe dyspnea is observed, the subject should be asked about other potential symptoms that could be linked to COVID-19 (e.g., fever) to act accordingly. If this is not possible a home nurse service should be organized to perform spirometry at the subject's home.
  - Visual disturbances: if reduced or blurred vision is reported, the investigator should consider whether waiting for site to return to normal site operation is acceptable. The investigator may consult the study ophthalmologist for the most appropriate action to be taken.
  - Symptoms that may indicate hepatotoxicity: (e.g., unusual lethargy or fatigue, nausea, vomiting, upper right quadrant pain or tenderness, jaundice, anorexia, dark urine, fever, rash, itching) blood sampling at home is to be conducted.
- Check for changes in any ongoing medication or start of new medication(s)
  - Check if the subject has enough study medication to ensure no study medication holiday.
  - Make sure that subjects who are women of childbearing potential have enough home pregnancy kits (send them along with study medications to subject's home if necessary) and remind them to perform the test monthly.
  - Ask the subject to perform the blood and urine sampling in a local laboratory for analysis using a prescription provided by the investigator\*\*.

\*\* If possible, in this situation laboratory results and reports should be sent to an "unblinded" site staff member who is not involved in the conduct of (ID-064A202) CARE study and who can check for any WBC (including differential) and lymphocyte count and redact these parameters from local laboratory report. If this option is not available, site local laboratory analysis results and reports should still be sent to the site.

- If closer monitoring of any of the above symptoms is not possible within the foreseeable future, depending on the severity of the symptoms observed and on the

investigator's assessment of the benefit-risk for the subject's participation in the trial, the investigator may consider discontinuing the study medication.

- A subject who permanently discontinues study treatment is not considered as having withdrawn from the study, provided that the subject's consent to participate in the study has not been withdrawn. Hence, the subject remains in the study, and study protocol assessments should continue to be performed until the end of the study following the planned scheduled of assessments. This will reduce the amount of missing data and should ensure data accuracy and scientific relevance of the study results.
- The site staff should organize the delivery of study treatment and pregnancy tests (if applicable) to the subject's home using either the institutional internal process or a home nurse, if allowed by local laws and regulation or by using the express courier service contracted by the sponsor. Shipment to subject's home can only occur after obtaining subject's consent [see Section 2.2.1].
- For those subjects for whom study medication is provided at home due to the inability to perform on-site visits, a solution must be identified to perform, at a minimum, the WBC and lymphocyte count assessments (preferably the entire chemistry and hematology panel) as close as possible to the original protocol schedule, preferably using the study central laboratory, or a local laboratory if necessary.
- During the remote visit, the investigator also ensures that the subject understands that the new study medication kit is to be used instead of the one used previously, even if there is remaining medication. The unused medication will have to be brought back to the center at the next safe opportunity.
- The **remote visit** must be entered as an **Unscheduled visit** in the eCRF and documented in detail (day, time and conversation) in the subject's medical charts.
- The remote visit is not meant to replace an on-site visit. If in the foreseeable future on-site visits can be resumed, planned on-site visits can be re-scheduled as long as the subject has enough study treatment and SLE background therapy. As soon as possible following the remote visit, the corresponding on-site visit must be performed. If the corresponding on-site visit can only be scheduled relatively close to the next scheduled study visit (e.g. within 1 week of the next study visit), this study visit will be skipped to the next scheduled on-site visit.

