## 2.4 Efficacy assessments

### 2.4.1 Study assessments related to the primary and secondary endpoints.

It is important to ensure that efficacy assessments, especially assessments related to primary (SLEDAI-2K) and secondary endpoints (i.e., BILAG and SRI-4) are performed as per protocol. They should ideally not be performed later than one month after the protocol planned schedule of assessment [see protocol section 7].

If the investigator is not able to arrange on-site visits to perform the planned efficacy evaluations, the following should be implemented:

- Organize the remote visit as described above, at approximately the time of the planned visit assessment.
- During the remote visit, the investigator should collect the SLEDAI-2K components even if not all assessments are possible [protocol section 7.2.6]. Record the outcome of the SLEDAI-2K assessment in the eCRF and report a PD related to COVID-19 in the event of missing values. If this is not possible, the investigator should contact the CRA or sponsor study team.
- The same procedures should be followed to perform the assessments (e.g., BILAG, PGA, SLE Flare Index) related to the secondary efficacy endpoints. These measurements should be collected at that time as well [protocol section 7.2.6].

**Very important note:** as soon as the study site can resume activity, ask the subject to come to the site at the closest scheduled visit, to perform a full SLEDAI-2K assessment and all other assessments (such as BILAG, PGA, ...) which will be recorded in the eCRF.

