After Month-6 analysis and Month-12 analysis, ongoing subjects will continue to be treated and followed up in a double-blinded manner up to their EOS visit. Investigators, site staff, subjects, and the sponsor staff responsible for the study conduct (with appropriate firewalls) will remain blinded to study treatment allocation until study closure.

To maintain the blinding of the study up to EOS analysis, two separate sponsor teams will be set up; Team 1 will be unblinded at the time of the Month-6 analysis while Team 2 will remain blinded in order to continue to review the data being collected up to EOS. The measures put in place to ensure the good conduct of this process will be described in a dedicated study document.

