6.8.3.3.1 Variables

The mSLEDAI-2K relevant disease characteristics are recorded and derived from the data on the mSLEDAI-2K eCRF page at Visit 1 (Screening), and the variables include:

- Presence / no presence of each active descriptor
- Mucocutaneous score
- Musculoskeletal score
- Sum of the mucocutaneous and musculoskeletal score
- mSLEDAI-2K total score
- SLEDAI-2K total score
- mSLEDAI-2K total score as a category (≥ 10 and < 10)
- SLEDAI-2K total score as a category (≥ 10 and < 10)

mSLEDAI-2K

The SLEDAI-2K is a disease activity index of SLE based on the presence of 24 descriptors in 9 organ systems over the preceding 10 days.

Descriptors of the SLEDAI-2K are documented as either present or absent (or not done). Each of the descriptors is weighted and the total score of SLEDAI-2K is the sum of all

24 (weighted) descriptor scores. The range of the total SLEDAI-2K score is 0 to 105, with higher scores representing higher disease activity.

In this study, a modified SLEDAI-2K (mSLEDAI-2K) score is applied. The item related to leukopenia is excluded from the SLEDAI-2K scoring due to the mode of action of the compound (i.e., lymphocyte count reduction in peripheral blood). Therefore, the mSLEDAI-2K total score has only 23 descriptors and a maximum score of 104.

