8.4.1 Measurements

The following parameters are assayed at any scheduled visit according to the protocol:

Hematology:

- Hemoglobin
- Hematocrit, mean corpuscular hemoglobin, mean corpuscular volume, and mean corpuscular hemoglobin concentration
- Erythrocyte count (reticulocyte count)
- Leukocyte count with differential counts (only available after database lock)
- Platelet count

Blood chemistry:

- Aspartate aminotransferase and alanine aminotransferase, alkaline phosphatase, total and direct bilirubin, lactate dehydrogenase
- Creatinine
- Blood urea nitrogen
- Uric acid
- Glucose
- Cholesterol, triglycerides
- Sodium, potassium, chloride, calcium
- Protein, albumin

Urinalysis (including but not limited to):

- pH

- Glucose
- Proteins
- Blood
- Leukocytes

Tests for tuberculosis, viral serology tests (Hepatitis B surface antigen, Hepatitis C antibodies, HIV1 and HIV2 antibodies, varicella-zoster virus IgG antibodies), coagulation tests (prothrombin time, international normalized ratio, activated partial thromboplastin time, urine-protein-to-creatinine ratio), other laboratory tests in the event of infection and pregnancy tests are also carried out during the study.

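### The COVID-19 addendum's last-resort laboratory route can show unredacted white-cell counts to efficacy raters, and no efficacy analysis named in the SAP is defined by that exposure

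*Protocol*

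**What the plan says.** **The route.** The addendum covers affected sites only, for as long as they are affected (Addendum section 1). At remote visits, subjects are asked to have blood and urine tested at a local laboratory. If possible, the results go to a staff member outside the study "who can check for any WBC (including differential) and lymphocyte count and redact these parameters from local laboratory report" (section 2.2). Without such a person the fallback is: "If this option is not available, site local laboratory analysis results and reports should still be sent to the site". The home-nurse paragraph carries the same footnote mark. The on-site counterpart in section 2.1 reads: "If this option is not available, the site local laboratory analysis should still be performed". For subjects supplied at home, testing must cover "at a minimum, the WBC and lymphocyte count assessments", with the central laboratory preferred.

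**Why the counts matter.** SAP 6.8.3.3.1 removes leukopenia from the score "due to the mode of action of the compound (i.e., lymphocyte count reduction in peripheral blood". SAP 8.4.1 lists "Leukocyte count with differential counts (only available after database lock". SAP 2.1 says that investigators and site staff "will remain blinded to study treatment allocation until study closure".

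**Who rates.** Addendum section 2.4.1: "During the remote visit, the investigator should collect the SLEDAI-2K components even if not all assessments are possible". It applies the same procedure to BILAG, PGA and the flare index.

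**What is reported.** SAP 6.6 tabulates COVID-19 deviations by category and subcategory, and lists unblinded subjects with the event behind the unblinding request. SAP 8.4 only lists local laboratory data. SAP 4.1.4 leaves the exact per-protocol exclusion reasons to a separate document.

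**The concern.** The plan takes deliberate steps to keep these counts away from sites, and the fallback removes that protection where no redactor exists. The primary endpoint and both secondary endpoints draw on ratings that the addendum assigns to the investigator. A rater who has seen a low lymphocyte count, and who expects the drug to work, may score an active subject more favourably and a placebo subject less so. That would bias the comparison towards cenerimod.

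The knowledge also lasts: a count seen at Month 2 is still known at Month 6. The relevant share is therefore every subject with an unredacted result before the Month 6 rating. Unless that share is recorded, nobody can later say whether it mattered, although Addendum section 1 gives reconstruction of the impact on trial integrity as the reason for tracking these deviations.

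**Working it through.** **1. Text check.** The documents give no figure to reproduce: no number of local-laboratory subjects, no expected rate of exposure and no standard deviation. I compared the route with the planned outputs.

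- SAP 6.6, listing of unblinded subjects: tied to an unblinding request, so a rater who merely sees a count would not appear in it.
- SAP 6.6, COVID-19 deviation tables: descriptive. The code list is not in the documents, so I cannot tell whether receipt of unredacted counts has its own subcategory.
- SAP Table 5 (primary endpoint): missing data, per-protocol set, complete cases, on-treatment data, full SLEDAI-2K, dose response, time course, subgroups. None is defined by site access to counts.
- SAP Tables 7 and 8 (SRI-4, BILAG-2004): per-protocol set, multiple imputation, tipping point, time course, subgroups. Again, none is.
- SAP 6.7.2, per-protocol exclusion categories: this exposure is not named, though the category for other reasons could hold it.

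**2. Illustrative size.**

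From the documents: about 325 subjects in five equal arms, so 325 / 5 = 65 per arm (SAP 2.1); 6% missing at Month 6 (SAP 7.2.3), so 65 × 0.94 = 61.1 evaluable; target difference 1.5 points (SAP 7.2.6.9.5); two-sided alpha 5% (SAP 7.2.5).

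Assumed, not in the documents: share f of Month 6 ratings made by an exposed rater, 5% to 20%; rating shift of 0.5 to 1 point in each direction, so the gap b between placebo and active is 1 to 2 points; SD 4 to 6.

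Formulas:

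- Bias = f × b
- SE = SD × √(2 / 61.1), which is 0.724 at SD 4 and 1.086 at SD 6
- Type I error of one comparison = Φ(−1.96 + bias/SE) + Φ(−1.96 − bias/SE), before Hochberg

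| f | b | Bias (points) | Share of 1.5 | Type I error, SD 6 to SD 4 |
|---|---|---|---|---|
| 5% | 1 | 0.05 | 3% | 0.050 to 0.051 |
| 10% | 2 | 0.20 | 13% | 0.054 to 0.059 |
| 20% | 2 | 0.40 | 27% | 0.066 to 0.086 |

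The formula takes every exposed guess as correct. If a share q of guesses is right in both arms, bias = f × b × (2q − 1), which falls to zero when guessing is no better than chance. For given f and b, the table is therefore an upper bound.

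**The case against.** **It is a last resort.** On-site visits and the central laboratory are preferred, home nurses ship samples to the central laboratory, and redaction comes first. SAP 8.4 calls local results exceptional. This stands, and it is why the frequency may be low. However, SAP 8.4 describes local testing for medical evaluation of an individual subject, which is not the addendum's reason for using it.

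**Exposure of the rater is inferred.** Section 2.2 sends reports to the site without saying who opens them, and section 2.1 says only that the analysis is done. This also stands. Exposure is plausible because section 2.4.1 makes the investigator the rater at remote visits, but it is not stated. The main protocol's blinding section was not among the documents.

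**The count is an imperfect signal.** Leukopenia is itself a SLEDAI-2K descriptor (SAP 6.8.3.3.1), so a low count can come from SLE in a placebo subject. This stands and reduces any bias.

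**Stronger readings to avoid.** A reader might infer that raters could identify the dose and that the bias grows with dose. The documents give no counts by dose, so neither follows. A reader might also conclude that no planned analysis can touch the problem. The per-protocol analyses cover the primary and both secondary endpoints, and their criteria might exclude such subjects; the SAP simply does not say so.

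**Conclusion.** The point holds in a limited form. Where local laboratories are used and no uninvolved person can redact, the addendum lets counts that the plan itself treats as revealing reach the site. An efficacy rater may then be able to guess active versus placebo, contrary to the blinding stated in SAP 2.1. The listing of unblinded subjects would not capture this, and no efficacy analysis named in the SAP is defined by it.

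The size is unknown. The range of 0.05 to 0.40 points rests wholly on assumed f and b, and the type I error figures also rest on an assumed SD. The upper end needs a fifth of Month 6 ratings to be exposed and every guess to be right. It should not be read as an estimate, or as evidence that the trial was unblinded. It does show that the answer depends on a number that can be collected.

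**What to change.** 1. **Routing.** Where no uninvolved redactor exists, have local reports received and redacted by a site staff member who does not score efficacy, where one is available. Safety testing is unchanged.
2. **Recording.** Record each subject and date on which unredacted counts reached an efficacy rater, and report the numbers by arm. This shows first whether the issue is trivial.
3. **Analysis.** Pre-specify a sensitivity analysis of the primary and two secondary endpoints with the existing models, setting ratings after that date to missing. If the data are already unblinded, label it post hoc.

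**Cost.** One dated flag, one table and one rerun; the primary analysis is unchanged. The sensitivity analysis loses precision in proportion to the number exposed. Treating Month 6 alone, the SE grows by √(1/0.95) = 1.026 at 5% exposed and √(1/0.80) = 1.118 at 20%, or about 3% to 12%. It also conditions on a post-randomisation event linked to site and pandemic period, and relies on missing at random, so it supports the primary result and does not replace it.
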